### **Arthralgias/Myaglias**

Pain management will initially be done with acetaminophen or ibuprofen as tolerated, or opiates as indicated. For severe toxicity, IFN will be held for 3 weeks and dose reduced according to Table 2. If not resolved to CTCAE grade 1 or better, patient will be removed from the study.

### **Weightloss**

If patient weightloss occurs  $>10\%$  of initial body weight, then IFN alpha will be held for 3 weeks. Weight gaining medications such as megace, marinol, and mirtazapine are acceptable. Patients will be dose reduced according to Table 2. If weight does not stabilize or start to recover within 3 weeks, patients will be withdrawn from the study

### **Depression**

For moderate depression grade 1 or 2, patients may be started on SSRI therapy as necessary. Any acute grade 3 or 4 reaction (psychosis, mania, suicidal ideation), IFN alpha will be stopped for 3 weeks. Patients can be restarted at reduced doses according to Table 2. If toxicities do not resolve to CTCAE grade 1 or better within 3 weeks, patients will be withdrawn from the study. Referral for acute hospitalization or psychiatric consultation will be placed for any life-threatening events.

### **GI Toxicity**

Nausea, vomiting, or both may be controlled with antiemetic therapy. Diarrhea should be treated with standard medications to avoid dose modification or interruption, if possible. Electrolyte supplementation with regular laboratory monitoring should be used, when appropriate, to maintain electrolytes within normal limits. For persistent Gr3/4 adverse events, pt will be dose reduced according to Table 2.

**TABLE 2: IFN alpha-2b dose levels**

Dose Level	IFN alpha-2b
-2	1 mcg/kg SQ q week per 21 day cycle
-1	2 mcg/kg SQ q week per 21 day cycle
0 ( starting dose)	3 mcg/kg SQ q week per 21 day cycle

**6. PHARMACEUTICAL INFORMATION**

5-FU/Capecitabine and IFN are commercially available and will be used from commercial suppliers.

**6.1 Expected potential toxicities of 5-FU/Capecitabine:**

Hematologic: anemia, neutropenia, thrombocytopenia

Constitutional: fatigue, pyrexia, edema, pain, chest pain

Dermatologic: hand-foot syndrome, dermatitis, skin discoloration, alopecia, nail disorders

Gastrointestinal: diarrhea, nausea, vomiting, stomatitis, abdominal pain, gastrointestinal motility disorder, constipation, oral discomfort, upper GI inflammatory disorders, gastrointestinal hemorrhage, ileus

Hepatic: hyperbilirubinemia

Infections: bacterial or viral

Metabolic: appetite decreased, dehydration

Musculoskeletal: back pain, arthralgia

Neurologic: peripheral sensory neuropathy, headache, dizziness, insomnia, taste disturbance

Ocular: eye irritation, vision abnormal

Psychiatric: mood alteration, depression

Pulmonary: dyspnea, cough, pharyngeal disorder, epistaxis, sore throat

Vascular: venous thrombosis

Cardiac: myocardial infarction/ischemia, angina, dysrhythmias, cardiac arrest, cardiac failure, sudden death, electrocardiographic changes, and cardiomyopathy.

Dihydropyrimidine Dehydrogenase Deficiency: Rarely, unexpected, severe toxicity (eg, stomatitis, diarrhea, neutropenia and neurotoxicity) associated with 5-fluorouracil has been attributed to a deficiency of dihydropyrimidine dehydrogenase (DPD) activity.

**6.2 Expected potential toxicities of IFN alpha-2b:**

General: "Influenza-like" symptoms (mainly fever, headache, chills, myalgia, and fatigue)

Gastrointestinal: anorexia, nausea, diarrhea, vomiting, altered taste, abdominal pain, constipation, gingivitis, loose stools, dyspepsia

Hepatic: elevated SGOT, right upper quadrant pain

Psychiatric: depression, anxiety, nervousness

Dermatologic: alopecia, rash, pruritus, dry skin, dermatitis, hair discoloration

Respiratory: dyspnea, coughing, pharyngitis, sinusitis, nonproductive cough, nasal congestion, and bronchitis

Nervous system: headache, somnolence, dizziness, irritability, paresthesia, impaired concentration, amnesia, confusion, insomnia, hypoesthesia, vertigo, and decreased libido

Musculoskeletal: myalgia, musculoskeletal pain, and arthralgia  
Immunologic: nonspecific infection, viral infection, and herpes simplex  
Hematologic: neutropenia, anemia, thrombocytopenia, bleeding, and purpura  
Genitourinary: Amenorrhea, polyuria  
Cardiovascular: hypertension. Angina, arrhythmia, atrial fibrillation, bradycardia, cardiac failure, cardiomegaly, cardiomyopathy, coronary artery disorder, extrasystoles, heart valve disorder, hematoma, hypotension, palpitations, phlebitis, postural hypotension, pulmonary embolism, Raynaud's disease, tachycardia, thrombosis, and varicose vein have been reported in less than 5% of patients.  
Endocrine: aggravation of diabetes mellitus, goiter, hyperthyroidism, and hypothyroidism in less than 5% of patients.  
Metabolic: Hypertriglyceridemia, dehydration, hypercalcemia, hyperglycemia, and  
Ocular: Ocular side effects have included abnormal vision, blurred vision, diplopia, dry eyes, eye pain, lacrimal gland disorder, lacrimation, nystagmus, and photophobia in less than 5% of patients.  
Renal: increased BUN and renal insufficiency in less than 5% of patients.  
Hypersensitivity: Hypersensitivity side effects have included allergic reaction  
Local: injection site inflammation

## 7. ADVERSE EVENTS: LIST AND REPORTING REQUIREMENTS

**Adverse Event:** Any untoward medical occurrence in a patient of clinical investigation subject administered a pharmaceutical product and which does not necessarily have to have a causal relationship with treatment. An adverse event (AE) can therefore be any unfavorable or unintended sign (including an abnormal laboratory finding), symptom, or disease temporally associated with the use of a medicinal product, whether or not considered related to the medicinal product.

### **Adverse Event Characteristics:**

**CTCAE term (AE description) and grade:** The descriptions and grading scales found in the revised NCI Common Terminology Criteria for Adverse Events (CTCAE) version 4.0 will be utilized for AE reporting. A copy of the CTCAE version 4.0 can be downloaded from the CTEP web site:

[http://ctep.cancer.gov/protocolDevelopment/electronic\\_applications/ctc.htm](http://ctep.cancer.gov/protocolDevelopment/electronic_applications/ctc.htm).

Hematologic and metabolic toxicities of Grade 1 and 2 will not be reported.

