### **5. DOSING DELAYS/DOSE MODIFICATIONS**

#### **5.1 5-FU/Capecitabine**

A dose reduction will be instituted upon any grade 3 or 4 toxicity that is attributable to 5-FU/capecitabine. For all grade 3 or 4 toxicities related to 5-FU/capecitabine, the study treatment will be withheld for up to 3 weeks until the toxicity has resolved to CTCAE grade 1 or better (or back to baseline), and then treatment may be restarted. Dose reduction/re-challenge for each toxicity criterion will be managed as discussed in the sections that follow. Patients will be withdrawn from the study if toxicity does not resolve to  $\leq$  CTCAE grade 1 (or to baseline) within 3 weeks.

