#### **Myelosuppression**

On Day 1 of each cycle, if the neutrophil count is  $< 1000/\text{mm}^3$ , or the platelet count is  $< 75,000/\text{mm}^3$ , then treatment with 5-FU/capecitabine will be held until the neutrophil count is  $\geq 1000/\text{mm}^3$ , and platelet count is  $\geq 75,000/\text{mm}^3$ . Once restarted, 5-FU/Capecitabine will be dose reduced per Table 1. If treatment is required to be held for  $\geq 3$  weeks, then study treatment will be discontinued.

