**Routine Adverse Event Reporting**

All adverse events **must** be reported in routine study data submissions using the data forms completed for each cycle of 5-FU/capecitabine and IFN treatment for entry by the study coordinator into the Oncore system.

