#### 11.1.2 Secondary Objective

To establish the progression free survival (PFS), overall survival (OS), and safety profile (AEs) of the combination of IFN alpha-2b and 5-FU/capecitabine in this patient population at 6 months and 1 year.

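### Section 7 both excludes low-grade hematologic toxicity and requires all adverse events to be reported; if the exclusion governs, platelet falls that change dosing could be missing from the safety table

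*Combined protocol and SAP*

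**What the plan says.** **Reporting.** Section 7 (Adverse Event Characteristics) adopts a grading scale, "Common Terminology Criteria for Adverse Events (CTCAE) version 4.0 will be utilized for AE reporting", and then limits what is reported: "Hematologic and metabolic toxicities of Grade 1 and 2 will not be reported". Further on, Section 7 (Routine Adverse Event Reporting) says that all adverse events must "be reported in routine study data submissions using the data forms completed for each cycle". It states no exception. The definition that opens Section 7 counts an abnormal laboratory finding as an adverse event.

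**Dosing.** Section 5.1 (Myelosuppression) holds 5-FU/capecitabine when the day-1 neutrophil count is below 1,000/mm3 or the platelet count is below 75,000/mm3. No grade is mentioned. After recovery, "Once restarted, 5-FU/Capecitabine will be dose reduced per Table 1"; Table 1 gives 600 and 400 mg/m2 below the 800 mg/m2 starting level. If a hold runs to three or more "weeks, then study treatment will be discontinued".

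**Analysis.** Section 11.1.2 makes the "safety profile (AEs) of the combination of IFN alpha-2b and 5-FU/capecitabine" a secondary objective. Section 11.4 plans a cumulative tabulation of adverse events. The text available describes no summary of holds, reductions or discontinuations by cause.

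**The concern.** The dosing rule is triggered by a count and the reporting rule by a grade. Where they do not line up, an event can change a patient's treatment and still fall below the reporting threshold. A reader of the safety table would then see less treatment-limiting thrombocytopenia than occurred.

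The protocol's own facts make such counts plausible. The platelet floor for eligibility in Section 3.1.7 (75,000/mcL) equals the hold threshold, so a patient who enters at the floor is held after any fall seen on day 1. Section 3.2.8 admits patients with CLL and other hematologic malignancies. Sections 6.1 and 6.2 list thrombocytopenia as expected with both drugs. The Rationale cites a more intensive phase I regimen, containing interferon and 5-FU, that cytopenias kept from being given in full. Tolerability with respect to blood counts is therefore something this trial should be able to describe.

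**Working it through.** The plan states no figure on this point, so there is none to reproduce. The check compares the rules and then varies the one missing input.

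**Step 1: which reporting rule governs?**
- If the routine-reporting paragraph governs, every low platelet count that meets the adverse event definition is reported. Nothing is lost, but the grade 1-2 exclusion has no effect.
- If the exclusion is a specific exception to the general rule, grade 1-2 hematologic events are not reported. This reading is plausible: the exclusion stands ahead of both the expedited and the routine paragraphs and is not confined to either.

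The documents do not say which applies. Steps 2 to 4 follow the second reading.

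**Step 2: the unreported platelet band.** Let L be the lower limit of grade 2, so that counts below L are grade 3 or worse and are reported. The documents do not print L. Band width = 75,000 − L, or zero if L is 75,000 or more.

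| Assumed L (per mm3) | Band with hold but no report | Width |
|---|---|---|
| 25,000 | 25,000 to <75,000 | 50,000 |
| 50,000 (working assumption for CTCAE v4.0) | 50,000 to <75,000 | 25,000 |
| 60,000 | 60,000 to <75,000 | 15,000 |
| 75,000 | none | 0 |

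The gap closes only if grade 3 already starts at 75,000.

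**Step 3: neutrophils.** The hold trigger is below 1,000/mm3. If grade 3 starts below 1,000 (also an assumption), every triggering count is reportable: 1,000 − 1,000 = 0. A limit of 1,500 likewise leaves no gap; a limit of 500 would leave a band of 500. On the working assumption the issue is confined to platelets.

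**Step 4: illustration of size.** Let q be the share of patients with at least one day-1 count in the band. The documents give no q. With the planned total enrolment of 30 (Section 11.2), expected patients = 30q, and the chance of at least one = 1 − (1 − q)^30.

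| Assumed q | Expected patients | Chance of at least one |
|---|---|---|
| 2% | 0.6 | 0.455 |
| 5% | 1.5 | 0.785 |
| 10% | 3.0 | 0.958 |
| 20% | 6.0 | 0.999 |

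**Step 5: a related mismatch in Section 5.1.** The opening paragraph ties dose reduction to grade 3 or 4 toxicity, with restart allowed after holding "until the toxicity has resolved to CTCAE grade 1 or better (or back to baseline), and then treatment may be restarted", and defers detail to the sections that follow. Myelosuppression then uses counts alone. If 50,000 to <75,000 is grade 2, it requires a reduction below the grade named in the opening paragraph. The two passages need to be reconciled; this review takes no position on which threshold should apply.

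**The case against.** The strongest reply is that the key link is not in the documents. No platelet grade is printed, and L cannot be inferred from the restart thresholds. It is tempting to match recovery to grade 1 with restart at 75,000, but the same match would make a neutrophil count of 1,000 grade 1, which conflicts with the assumption in Step 3. Nor does describing 75,000 or more as normal marrow function in Section 3.1.7 set a grade boundary. This stands: the grade 2 band remains an assumption.

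Second, a direct conflict between two reporting rules makes the outcome indeterminate; it does not make omission certain. This also stands. A reader might infer that the safety table will omit every dose-limiting count in the band. That follows only if the exclusion overrides the routine-reporting paragraph.

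Third, other records exist. Section 8 schedules a CBC with differential at the start of each cycle shown, forms are completed each cycle, and an event meeting the serious criteria still follows the SAE route. The case report forms are not in the documents, so it cannot be said that reductions will appear without any recorded cause. What remains is that Section 11.4 plans no analysis of those counts or of dose changes.

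Fourth, leaving out low-grade laboratory events is a deliberate and reasonable economy in a small single-arm response trial. That is accepted. The economy does not require leaving out the few events that alter treatment.

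**Conclusion.** The reporting rules in Section 7 conflict and should be reconciled. If the grade 1-2 exclusion governs, and if grade 2 extends below 75,000/mm3, a platelet count that compels a hold and a lower dose need not enter the adverse event data. The same holds for one that ends treatment after a three-week hold. The Section 11.4 tabulation could then under-count treatment-limiting thrombocytopenia.

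The size cannot be stated, because Step 4 rests on assumed frequencies. A reader might go further and conclude that a definite number of events will be lost, or that the combination will look safer than it is. The documents give no incidence and do not settle which rule prevails, so neither conclusion is supported. The steps are also unequal: one hold leads to one reduction, whereas reaching 400 mg/m2 takes two reductions and discontinuation takes a hold of at least three weeks.

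The point concerns a secondary objective and, on the working assumption, platelets only. Grade 3-4 hematologic events are still reported. The response endpoint, the two-stage rule and the sample size are untouched.

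**What to change.** 1. In Section 7 (Adverse Event Characteristics), state that grade 1 and 2 hematologic and metabolic toxicities are not reported unless they lead to a hold, dose reduction or discontinuation of either drug.
2. In Section 7 (Routine Adverse Event Reporting), make the all-events requirement subject to that same rule, so that one instruction applies.
3. In Section 11.4, add a table of dose holds, reductions and discontinuations by drug and by cause.
4. Reconcile the opening paragraph of Section 5.1 (grade-based trigger) with its Myelosuppression paragraph (count-based trigger). No clinical threshold is proposed or changed here.

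The cost is a few more adverse event entries, drawn from day-1 counts already scheduled, and one extra table. Routine low-grade laboratory findings with no effect on treatment stay excluded.

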### **Expedited Serious Adverse Event (SAE) Reporting:**

A SAE is any sign, symptom or medical condition that emerges during treatment or during a post-treatment follow-up period that (1) was not present at the start of treatment and it is not a chronic condition that is part of the patient's medical history, OR (2) was present at the start of treatment or as part of the patient's medical history but worsened in severity and/or frequency during therapy, AND that meets any of the following regulatory serious criteria:

- Results in death
- Is life-threatening
- Requires or prolongs inpatient hospitalization
- Is disabling

- Is a congenital anomaly/birth defect
- Is medically significant or requires medical or surgical intervention to prevent one of the outcomes listed above.

**All SAEs should be recorded on a MedWatch 3500a Form and delivered to:**

The study coordinator will submit the SAE for review to the PI and to the institutional IRB (per the SOP of the Moffitt Cancer Center clinical trials office).

**Routine Adverse Event Reporting**

All adverse events **must** be reported in routine study data submissions using the data forms completed for each cycle of 5-FU/capecitabine and IFN treatment for entry by the study coordinator into the Oncore system.

**8. STUDY CALENDAR**

Baseline evaluations are to be conducted within 2 week prior to administration of protocol therapy. Scans and x-rays must be done <=4 weeks prior to the start of therapy. In the event that the patient's condition is deteriorating, laboratory evaluations should be repeated within 48 hours prior to initiation of the next cycle of therapy. Estimated time per treatment visit is 1 hour.

		Cycle 1			Cycle 2			Cycle 3			
	Pre-Study	Wk 1	Wk 2	Wk 3	Wk 4	Wk 5	Wk 6	Wk 7	Wk 8	Wk 9	Off Study c
Capecitabine		X	X		X	X		X	X		
5-FUd		X			X			X			
IFN alpha-2b		X	X	X	X	X	X	X	X	X	
Informed consent	X										
Pregnancy Testing	X										
Demographics	X										
Medical history	X										
Concurrent meds	X	X-----X									
Physical exam	X	X			X			X			X
Vital signs a	X	X			X			X			X
Height	X										
Weight	X	X			X			X			X

ECOG/Performance status	X	X			X			X			X
CBC w/diff	X	X			X			X			X
Serum chemistry b	X	X			X			X			X
EKG (as indicated)	X										
Adverse event evaluation					X-----X						X
Tumor measurements	X										
Radiologic evaluation	X										

a= Blood Pressure, Heart Rate (Pulse), Temperature,

b= Albumin, alkaline phosphatase, total bilirubin, bicarbonate, BUN, calcium, chloride, creatinine, glucose, , potassium, total protein, SGOT[AST], SGPT[ALT], sodium

c= Off-study evaluation to be conducted within 30 days of last dose (+/- 7 days).

d= patients will be on either 5-FU infusion treatments or capecitabine, not both

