### **3. PATIENT SELECTION**

#### **3.1 Inclusion Criteria**

- 3.1.1 Patients must have histologically or cytologically confirmed squamous cell carcinoma of the skin. Patients who present with "squamous cell carcinoma of unknown primary lesions" at the time of diagnosis will be eligible if patients have a plausible primary skin site removed in the past. Similarly, patients with neck, parotid, or facial lymph nodes positive for squamous cell carcinoma with no identifiable mucosal primary would also be eligible.

- 3.1.2 Patients must have measurable disease, defined by RECIST v1.1 as at least one lesion that can be accurately measured in at least one dimension of  $\geq 10$  mm by CT, MRI, or calipers. See section 9.2 for the evaluation of measurable disease.
- 3.1.3 There is no limitation to prior treatments with local, regional, topical or systemic agents, except for prior systemic treatment with 5-fluorouracil or prodrugs thereof. Prior topical treatment with 5-fluorouracil is permitted. Patients who are on chronic daily doses of prednisone of greater than 10 mg are excluded. There is no restriction on timing of last treatments as long as patients have recovered from all expected toxicities and at least 21 days have passed since last administration.
- 3.1.4 Age  $\geq 18$  years. Because no dosing or adverse event data are currently available on the use of 5-FU/Capecitabine or IFN alpha-2b in patients  $<18$  years of age, children are excluded from this study.
- 3.1.5 Life expectancy of greater than 3 months.
- 3.1.6 ECOG performance status  $\leq 2$  (Karnofsky  $\geq 60\%$ ; see Appendix A).
- 3.1.7 Patients must have normal organ and marrow function as defined below:
 

Absolute neutrophil count	$\geq 1,500/\text{mcL}$
Platelets	$\geq 75,000/\text{mcL}$
Total Bilirubin	$< \text{ULN}$ or up to 2x ULN if patient has clinically documented Gilbert's syndrome (elevated unconjugated bilirubin from decreased UGT1A1 activity)
AST(SGOT)/ALT(SGPT)	$\leq 2.5x$ institutional upper limit of normal or up to 5x ULN if known to be caused by liver metastasis
Creatinine Clearance	$\geq 50 \text{ mL/min}$ by either Cockcroft-Gault formula or 24 hr urine collection analysis.

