- 3.1.8 Patients must not be candidates for curative locoregional treatments. Patients with recurrent locoregional disease following surgery and/or radiation for who a resection is unacceptably morbid and unlikely to be curative are eligible. Patients must be reviewed at the Moffitt Cutaneous Tumor Board prior to enrolling on trial to verify unresectability.
- 3.1.9 The effects of 5-FU/Capecitabine and IFN alpha-2b on the developing

human fetus at the recommended therapeutic dose are unknown. For this reason and because anti-metabolites are known to be teratogenic, women of child-bearing potential and men must agree to use adequate contraception (barrier method of birth control; abstinence) prior to study entry and for the duration of study participation. Should a woman become pregnant or suspect she is pregnant while participating in this study, she should inform her treating physician immediately.

3.1.10 Ability to understand and the willingness to sign a written informed consent document.

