### 3.2 Exclusion Criteria

3.2.1 Patients who have had chemotherapy or radiotherapy within 21 days (6 weeks for nitrosoureas or mitomycin C) prior to entering the study or those who have not recovered from adverse events due to agents administered more than 3 weeks earlier.

3.2.2 Patients may not be receiving any other investigational agents.

3.2.3 Patients with known brain metastases should be excluded from this clinical trial because of their poor prognosis and because they often develop progressive neurologic dysfunction that would confound the evaluation of neurologic and other adverse events.

3.2.4 History of allergic reactions attributed to compounds of similar chemical or biologic composition to either 5-FU/Capecitabine or Interferon.

3.2.5 Uncontrolled, ongoing illness including, but not limited to, ongoing or active infection, symptomatic congestive heart failure, unstable angina pectoris, myocardial infarction <30 days, CVA/TIA <30 days, cardiac arrhythmia, or psychiatric illness/social situations that would limit compliance with study requirements.

3.2.6 Pregnant women are excluded from this study because 5-FU/Capecitabine is an anti-metabolite agent with the potential for teratogenic or abortifacient effects. Because there is an unknown but potential risk for adverse events in nursing infants secondary to treatment of the mother with 5-FU/Capecitabine, breastfeeding should be discontinued if the mother is treated with 5-FU/Capecitabine. Pregnancy testing will be completed on all female participants of child-bearing potential by urine analysis.

3.2.8 Any heart or lung transplant patient on immunosuppressive agents. Renal transplant patients are allowed if patient is willing to reduce immunosuppressive agents and understand risk of rejection and possible need to return to dialysis. Patients with CLL or other hematologic malignancies are allowed as long as they meet other criteria listed above.

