### 9.1.3 Target lesions

All measurable lesions up to a maximum of five lesions per organ and 10 lesions in total, representative of all involved organs, should be identified as **target lesions** and recorded and measured at baseline. Target lesions should be selected on the basis of their size (lesions with the longest diameter) and their suitability for accurate repeated measurements (either by imaging techniques or clinically). A sum of the longest diameter (LD) for all target lesions will be calculated and reported as the baseline sum LD. The baseline sum LD will be used as reference by which to characterize the objective tumor response.

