## 9.2 Guidelines for Evaluation of Measurable Disease

All measurements should be taken and recorded in metric notation using a ruler or calipers. All baseline evaluations should be performed as closely as possible to the beginning of treatment and never more than 4 weeks before the beginning of the treatment.

The same method of assessment and the same technique should be used to characterize each identified and reported lesion at baseline and during follow-up. Imaging-based evaluation is preferred to evaluation by clinical examination when both methods have been used to assess the antitumor effect of a treatment.

**Clinical lesions.** Clinical lesions will only be considered measurable when they are superficial (e.g., skin nodules and palpable lymph nodes). In the case of skin lesions, documentation by calipers or color photography (including a ruler to estimate the size of the lesion) is recommended.

**Conventional CT and MRI.** These techniques should be performed with cuts of 10 mm or less in slice thickness contiguously. Spiral CT should be performed using a 5 mm contiguous reconstruction algorithm. This applies to tumors of the chest, abdomen, and pelvis. Head and neck tumors and those of extremities usually require

specific protocols.

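### The baseline scan can predate the end of earlier chemotherapy or radiotherapy, and a recently irradiated lesion can be a target, so carry-over shrinkage may be scored as response.

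*Combined protocol and SAP*

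**What the plan says.** **Baseline timing.** Section 8 sets two windows. General assessments: "Baseline evaluations are to be conducted within 2 week prior to administration of protocol therapy". Imaging: "Scans and x-rays must be done <=4 weeks prior to the start of therapy". Section 9.2 advises performing all baseline evaluations as near to treatment as feasible and sets the outer limit as "never more than 4 weeks before the beginning of the treatment".

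**Washout.** Section 3.2.1 excludes "Patients who have had chemotherapy or radiotherapy within 21 days (6 weeks for nitrosoureas or mitomycin C) prior to entering the study". Section 3.1.3 says "There is no limitation to prior treatments with local, regional, topical or systemic agents", apart from systemic 5-fluorouracil and its prodrugs, and asks for recovery from toxicity and that "at least 21 days have passed since last administration". Section 3.1.8 names as eligible "Patients with recurrent locoregional disease following surgery and/or radiation" when resection is too morbid and unlikely to cure.

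**Targets and response.** Section 9.1.3 takes as targets "All measurable lesions up to a maximum of five lesions per organ and 10 lesions in total". It has no rule for a lesion in an irradiated field. The baseline sum is the reference for response, and Section 9.3.1 defines partial response as a fall of at least 30% from it. Section 9.4.1 asks for confirmation 4 weeks later.

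**Decision.** Section 11.2 is a single-arm Simon two-stage design, 10% against 30%, with both error rates set at 0.1: at least 2 responses in 16 to continue, at least 5 in 25 to declare interest.

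**The concern.** The scan window is longer than the washout, and nothing orders the scan after the last prior treatment. A patient can comply with every rule and still have a baseline sum recorded while earlier therapy was under way. Separately, a lesion irradiated a few weeks before entry can be a target even if it is still shrinking from that radiotherapy. Section 9.4.1 gives no protection, because the confirmatory measurement is compared with the same baseline.

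With no control arm, nothing separates late shrinkage from the effect of the study regimen. With a threshold of 5 in 25, one or two misattributed responses can change the conclusion.

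**Working it through.** **1. Overlap of the windows.** Let g be the days from study entry to first dose. The scan may be 28 days before first dose; the last prior treatment may be 21 + g days before it. Overlap = 28 − (21 + g) = 7 − g.

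| g (days) | Overlap (days) |
|---|---|
| 0 | 7 |
| 3 | 4 |
| 7 or more | 0 |

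For nitrosoureas and mitomycin C (42 days) there is no overlap.

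**2. How carry-over lowers the bar.** Set the recorded baseline sum at 100, so partial response needs 70 or less. If earlier treatment removes x after the scan, the study regimen must supply a further fall of 1 − 70/(100 − x).

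- x = 10: 1 − 70/90 = 22.2%
- x = 20: 1 − 70/80 = 12.5%

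This applies with or without overlap, provided shrinkage continues after the scan.

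**3. The plan's own design.** With X1 ~ Bin(16, p) and X2 ~ Bin(9, p), P(declare) is the sum over x ≥ 2 of P(X1 = x) · P(X2 ≥ 5 − x). At p = 0.10 this is 0.0951; at p = 0.30 it is 0.9030. Both meet the stated error rates, so the design reproduces.

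**4. Illustrative effect at a true rate of 10%.** Let f be the share of patients with a recently treated target and c the chance that such a patient, otherwise a non-responder, is scored a responder. Apparent rate = 0.10 + f × 0.90 × c. Both f and c are assumptions; the documents give neither.

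| f | c | Apparent rate | P(declare interest) |
|---|---|---|---|
| 0 | – | 0.1000 | 0.095 |
| 2% | 10% | 0.1018 | 0.101 |
| 2% | 30% | 0.1054 | 0.113 |
| 5% | 30% | 0.1135 | 0.14 |
| 5% | 50% | 0.1225 | 0.18 |
| 10% | 30% | 0.1270 | 0.20 |
| 10% | 50% | 0.1450 | 0.285 |

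**5. One misattributed patient.** Suppose exactly one of the 25 is scored a responder through carry-over and the other 24 respond at 10%. P(declare) is then 0.21 if that patient is in stage 1 and 0.20 if in stage 2, about double 0.095. This needs no f or c, but it assumes that such a patient is present.

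**The case against.** **Timing.** Seven days is a ceiling. The washout runs to study entry and the scan window to start of therapy, and access steps that the protocol mentions (insurance approval for capecitabine, port placement for infusional 5-FU) could lengthen the gap, although the protocol does not say whether they precede entry. Section 9.2 also urges scans close to treatment. Both points reduce how often overlap occurs. Neither rules it out, because the Section 9.2 wording is advice and sets no order relative to prior therapy.

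**Caliper lesions.** On one reading of Section 8, skin lesions measured clinically fall under the 2-week window and so are measured after the washout. That is arguable, since Section 9.2 allows 4 weeks for every baseline evaluation.

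**Direction.** A reader might infer that the error can only add responses. That does not follow. An old scan also misses growth before day 1, which makes a 30% fall from the recorded sum harder to reach. Carry-over inflates response; staleness as such can act either way.

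**Frequency.** A reader might also infer from Section 3.1.8 that recent radiotherapy is common here. That section describes an eligible group and gives no frequency. It also speaks of disease that has recurred after treatment, which is some protection for that group. It does not require growth of each target lesion, nor does it cover metastatic patients or recent chemotherapy.

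**Size.** A carry-over response still needs a 30% fall in the whole target sum, no new lesions or non-target progression, and confirmation. Low shares are therefore plausible, and at f = 2% the error rate barely moves.

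**Conclusion.** The gap in the text is real. Following the plan exactly can give a baseline sum that predates the end of earlier treatment by up to 7 days, and it can make a recently irradiated lesion a target without evidence of growth. No other section closes this.

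The size is not established. The probability of declaring an inactive regimen of interest ranges from about 0.10 to 0.29 over the assumed shares, against 0.095 as designed. The documents do not support reading the upper figures as an estimate of the trial's false-positive rate: they rest on assumed inputs, and none of them derives from the 7-day overlap. The single-patient result (0.20 to 0.21) shows that the decision rule is sensitive, not that such a patient is likely.

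Severity is minor to moderate. Confidence is high on the text and low on the size.

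**What to change.** 1. **Sections 8 and 9.2:** require all baseline tumour measurements, by imaging or calipers, to be taken after the last dose or fraction of any prior anticancer therapy and still within the existing 4 weeks before treatment.
2. **Section 9.1.3:** allow a lesion in a previously irradiated field as a target only if growth since that radiotherapy is documented; otherwise record it as non-target.
3. **Section 11:** add a sensitivity analysis of the response rate excluding recently treated patients, with the interval that counts as recent fixed in advance. This is needed because the first change removes the overlap but not shrinkage that continues after a later scan, and the second does not address prior chemotherapy.

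The sample size, thresholds and primary analysis stay as they are. The cost is a short amendment, later scan timing for a few patients, and an occasional patient left without an acceptable target lesion under the measurable-disease criterion in Section 3.1.2. The sensitivity analysis needs the date of last prior treatment for each patient and will have fewer than 25 patients if any are excluded, so it should be read as supportive.
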